Ixazomib for Desensitization (IXADES)

NCT03213158

PI: [name]
6-3-2019

CLINICAL STUDY PROTOCOL

Protocol Number: IISR-2014-100831

Ixazomib for Desensitization (IXADES)

Indication: Sensitization in Kidney Transplant Candidates
Phase: II

Protocol Version 3 June 2019

Investigator and Study Center:

Principal Investigator: [name]
Professor
Department of Medicine-Nephrology
[name]
[name]
[name]
[contact]
Email: [contact]

UW IRB #: 2017-0429

Sub-Investigator(s): [name], NP
[name]
[name]
[name]

Collaborators: [name]
[name]
University of Michigan
Department of Surgery
Biomedical Sciences Research Bldg.
[name]
[name]
[name]

Outside Laboratory Services: Terasaki Foundation Laboratory
[name]
[name]
[name]

Local Laboratory Services: UW Health-University of Wisconsin Hospital and Clinics
Clinical Laboratories
[name]
[name]

ICTR Data Monitoring Committee Contact:

[name], MS
[name]
School of Medicine and Public Health
[name]
Email: [contact]

ICTR Study Monitoring Service Contact:

[name]
School of Medicine and Public Health
[name]
Ph: [contact]

Funding Agency: This is an investigator-initiated study, funded by Millennium Pharmaceuticals, Inc., a wholly owned subsidiary of Takeda Pharmaceutical Company Limited. The principal investigator [name], (who may also be referred to as the sponsor-investigator), is conducting the study and acting as the sponsor. Therefore, the legal/ethical obligations of the principal investigator include both those of a sponsor and those of an investigator.

PROTOCOL SUMMARY

[figure not shown]
This is a pilot exploratory, proof of concept, open-label, single-center phase II investigator initiated clinical trial entitled IXAzomib for DESensitization (IXADES). The purpose of the study is (1) to examine the safety and efficacy of ixazomib for desensitization of highly sensitized kidney transplant candidates and (2) to conduct mechanistic studies to address the role of HLA and non-HLA antibodies, T and B cell phenotypes, and BAFF/APRIL in immune monitoring of sensitized kidney transplant candidates (Figure 1).

Specific Aim 1. To determine the safety and efficacy of ixazomib as a desensitization strategy. There is currently no effective desensitization strategy for highly sensitized patients defined as calculated Panel of Reactive Antibodies (cPRA) $\geq 80\%$. For this study, 10 highly sensitized kidney transplant candidates on the waitlist for more than 24 months will receive ixazomib 3 mg (and dexamethasone 20 mg) on days 1, 8, and 15 of a 28 cycle for 12 months. The primary objective is to evaluate the safety (distal neuropathy, thrombocytopenia, and gastrointestinal symptoms) and efficacy (decline in cPRA $> 20\%$) of ixazomib. The secondary efficacy endpoint is transplantation rate within 12 months of therapy.

Specific Aim 2. Identify immune indices which predict the course of disease and/or response to treatment in highly sensitized patients. Mechanistic studies will use bone marrow and blood obtained from subjects in Aim 1 to determine the effect of treatment on immune regulation and reconstitution after therapy. Since the bone marrow microenvironment produces BAFF/APRIL and supports plasma cell maturation, we will determine the effect of therapy on the generation of BAFF/APRIL by bone marrow mesenchymal stem cells and the survival of bone marrow-derived plasma cells after desensitization. We specifically propose to:

- Identify if bone marrow plasma cells, IgG subsets, and levels including free light chains, and circulating BAFF/APRIL predict outcomes.
- Determine if treatment is effective in downregulating circulating BAFF/APRIL and anti-HLA, endothelin-1 type A receptor (ETAR), angiotensin type 1 receptor (AT1R), and complement fixing C1q antibodies.

Figure 1. Protocol Summary

| |
|--|
| Study Title: IXAzomib for DESensitization (IXADES) |
| Phase: II |
| Number of Patients: 10 |
| Study Objectives The primary objective is to evaluate the efficacy of ixazomib in desensitizing highly sensitized kidney transplant recipient, defined as a decline in calculated PRA (cPRA) > 20%, or successful transplantation within 12 months. The secondary objective is to determine the toxicity and tolerability of ixazomib with particular focus on distal neuropathy, thrombocytopenia, and gastrointestinal symptoms. |
| Overview of Study Design: We will examine the safety and efficacy of ixazomib for desensitization of highly sensitized kidney transplant candidates and conduct mechanistic studies to address the role of IgG subclasses, IgG complement binding capacity, non-HLA antibodies, T and B cell phenotypes, and BAFF/APRIL in immune monitoring and regulation. |
| 
 • Primary efficacy and safety endpoint: 
 ○ Efficacy endpoint: A decline in cPRA > 20%. ○ Safety endpoint: infections, malignancies, hematological complications including leucopenia, anemia, and thrombocytopenia, cardiovascular complications and events, distal neuropathy, gastrointestinal symptoms, and immunosuppression-related adverse effects • Secondary efficacy endpoint: Successful transplantation within 12 months • Tertiary/Exploratory Endpoints/Correlataive studies: Defining a marker of disease activity in sensitized patients will have a significant impact on the future of desensitization protocols. Although DSA, cPRA, CDC and T cell and B cell flow crossmatch have been used to characterize the severity of sensitization, these assays are labor intensive and expensive. The proposed plasma BAFF/APRIL ELISA assays can be performed in 2-3 hours (1). We will determine whether these cytokines can reflect the immune response and predict response to desensitization and ultimately transplant outcome. In addition, we propose studies to address the effect of ixazomib on (a) bone marrow derived BAFF/APRIL generated by bone marrow-mesenchymal stem cells, knowing that these stromal cells play a key role during the maturation activation of plasma cells, (b) bone marrow-derived antibody secreting cells (plasma cells) (2) and (c) plasma IgG subclasses, anti-HLA, ETAR, AT1R, and C1q antibody response to treatment (3, 4). |

Study Population:

Patients will be recruited from our center. All patients must be **(1)** Male or female patients 18-70 years of age **(2)** Able to provide informed consent **(3)** Female patients who are postmenopausal for at least 1 year before the screening visit, or are surgically sterile, or If they are of childbearing potential, agree to practice 2 effective methods of contraception, at the same time, from the time of signing the informed consent form through 90 days after the last dose of study drug, OR agree to practice true abstinence when this is in line with the preferred and usual lifestyle of the subject. (Periodic abstinence [eg, calendar, ovulation, symptothermal, post-ovulation methods] and withdrawal are not acceptable methods of contraception.) **(4)** Male patients, even if surgically sterilized (ie, status post-vasectomy), must agree to one of the following: Agree to practice effective barrier contraception during the entire study treatment period and through 90 days after the last dose of study drug, or Agree to practice true abstinence when this is in line with the preferred and usual lifestyle of the subject. (Periodic abstinence (eg, calendar, ovulation, symptothermal, post-ovulation methods] and withdrawal are not acceptable methods of contraception.) **(5)** Patients must be highly sensitized with a cPRA $\geq 80\%$ **(6)** Be active on the waitlist for kidney transplantation > 24 months to confirm their inability to receive a deceased donor transplant because of their sensitization status **(7)** Patients must meet the following clinical laboratory criteria (a) Absolute neutrophil count (ANC) $\geq 1,000/\text{mm}^3$ and platelet count $\geq 75,000/\text{mm}^3$. Platelet transfusions to help patients meet eligibility criteria are not allowed within 21 days before study enrollment (b) Total bilirubin $\leq 1.5 \times$ the upper limit of the normal range (ULN) (c) Alanine aminotransferase (ALT) and aspartate aminotransferase (AST) $\leq 3 \times$ ULN.

Exclusion criteria: Patients will be excluded from the study based on the following criteria: **(1)** Female patients who are lactating or have a positive serum pregnancy test during the screening period **(2)** Major surgery requiring hospitalization within 6 months before enrollment **(3)** Infection requiring systemic antibiotic therapy or other serious infection within 14 days before study enrollment. **(4)** Evidence of current uncontrolled cardiovascular conditions, including uncontrolled hypertension, uncontrolled cardiac arrhythmias, symptomatic congestive heart failure, unstable angina, or myocardial infarction within the past 6 months **(5)** Systemic treatment, within 14 days before the first dose of ixazomib, with strong CYP3A inducers (rifampin, rifapentine, rifabutin, carbamazepine, phenytoin, phenobarbital), or use of St. John's wort. **(6)** Any serious medical or psychiatric illness that could, in the investigator's opinion, potentially interfere with the completion of treatment according to this protocol **(7)** Inability to take oral medication **(8)** Diagnosed or treated for another malignancy within 2 years before study enrollment or previously diagnosed with another malignancy and have any evidence of residual disease. Patients with nonmelanoma skin cancer or carcinoma in situ of any type are not excluded if they have undergone complete resection. **(9)** Grade 2 or greater peripheral neuropathy **(10)** Participation in other desensitization therapies or investigational drug clinical trials, including those with other investigational agents not included in this trial, within 6 months of the start of this trial and throughout the duration of this trial **(11)** Patients that have previously been treated with ixazomib, or participated in a study with ixazomib whether treated with ixazomib or not **(12)** Active or treated infection for HIV, HCV or HBV **(13)** History of liver cirrhosis, biopsy confirmed **(14)** Elevated transaminases (greater than 3 times the upper limit of normal) **(15)** Known hypersensitivity to ixazomib **(16)** Active substance abuse by self-report or medical record **(17)** Electrocardiography evidence of acute ischemia or active conduction system abnormalities

Duration of Study: Patients will be on study for one year, plus 1 month. For those transplanted, data on rejection, graft and patient survival will be collected for 6 months.

[figure not shown]
STUDY OVERVIEW DIAGRAM (optional)

Table 1-1 IXADES Treatment Protocol

| 28-Day Cycle (a 4-week cycle) | | | | | | | | |
|-------------------------------|--------|----------|--------|-----------|--------|------------|--------|------------|
| | Week 1 | | Week 2 | | Week 3 | | Week 4 | |
| | Day 1 | Days 2-7 | Day 8 | Days 9-14 | Day 15 | Days 16-21 | Day 22 | Days 23-28 |
| Ixazomib (NINLARO) 3 mg | ✓ | | ✓ | | ✓ | | | |
| Dexamethasone 20 mg | ✓ | | ✓ | | ✓ | | | |

Figure 1. Study Overview Diagram

Ixazomib for Desensitization (IXADES) in Kidney Transplantation

SCHEDULE OF EVENTS
Table 2-1 (a)-Schedule of events (first six cycles)

| Procedures Performed | Screening (<=/ 30 days) | Cycle 1 (< /= 3 months after screening) | | | Cycle 2 | | Cycle 3 | | | Cycle 4 | | | Cycle 5 | | | Cycle 6 | | |
|------------------------------------|-------------------------|---|---|----|---------|----|---------|----|----|---------|----|----|---------|-----|-----|---------|-----|-----|
| | | 1 | 8 | 15 | 29 | 36 | 43 | 57 | 64 | 71 | 85 | 92 | 99 | 113 | 120 | 127 | 141 | 148 |
| Treatment Days (+6, -3) | | | | | | | | | | | | | | | | | | |
| Ixazomib and Dexamethasone | | X | X | X | X | X | X | X | X | X | X | X | X | X | X | X | X | X |
| Medical History | X | X | | | | | | | | | X | | | X | | | X | |
| Physical Exam | X | X* | | | | | | | | | X | | | | | | | |
| Vital Signs (T, P, R, BP) | X | X | | | X | | | X | | | X | | | X | | | X | |
| AE Assessment | | X | | | X | | | X | | | X | | | X | | | X | |
| Electrocardiogram (ECG) | X | | | | | | | | | | | | | | | | | |
| Echocardiogram | X | | | | | | | | | | | | | | | | | |
| Medication History | X | X | | | X | | | X | | | X | | | X | | | X | |
| Drug Accountability | | | | | X | | | X | | | X | | | X | | | X | |
| Pregnancy Test (where appropriate) | X | | | | | | | | | | | | | | | | | |
| CBC | X | X | | | X | | | X | | | X | | | X | | | X | |
| LFTs | X | X | | X | X | | X | X | X | | X | | | X | | | X | |
| cPRA | | X | | | | | | | | | X | | | | | | | |
| BAFF/APRIL | | X | | | | | | | | | X | | | | | | | |
| DSA Antibodies | | X | | | | | | | | | X | | | | | | | |
| Bone Marrow Aspiration | | X ¹ | | | | | | | | | | | | | | | | |

*Physical examination to be completed at visit 1, if not completed during screening visit.

1 Bone Marrow Aspiration must be done before drug administration and at one of the following endpoints: one month (+6, -3 days) after the end of the 12 month study, cPRA decline > 20%, time of transplant, or time of subject withdrawal from the study.

Table 2-1 (b)-Schedule of events (last six cycles)

| Procedures Performed | Cycle 7 | | | Cycle 8 | | | Cycle 9 | | | Cycle 10 | | | Cycle 11 | | | Cycle 12 | | | Final visit 1M after last dose | ETV or Unscheduled Visit |
|------------------------------------|---------|-----|-----|---------|-----|-----|---------|-----|-----|----------|-----|-----|----------|-----|-----|----------|-----|----------------|--------------------------------|--------------------------|
| Treatment Days | 169 | 176 | 183 | 197 | 204 | 211 | 225 | 232 | 239 | 253 | 260 | 267 | 281 | 288 | 295 | 309 | 316 | 323 | 373 | |
| Ixazomib and dexamethasone | X | X | X | X | X | X | X | X | X | X | X | X | X | X | X | X | X | X | | |
| Medical History | X | | | | | | | | | X | | | | | | | | | X | |
| Physical Exam | X | | | | | | | | | X | | | | | | | | | X | |
| Vital Signs (T, P, R, BP) | X | | | X | | | X | | | X | | | X | | | X | | X | X | |
| AE Assessment | X | | | X | | | X | | | X | | | X | | | X | | X | X | |
| Electrocardiogram (ECG) | X | | | | | | | | | | | | | | | | | | X | |
| Echocardiogram | X | | | | | | | | | | | | | | | | | | X | |
| Medication History | X | | | X | | | X | | | X | | | X | | | X | | X | X | |
| Drug Accountability | | | | X | | | X | | | X | | | X | | | X | | X | X | |
| Pregnancy Test (where appropriate) | | | | | | | | | | | | | | | | | | | | |
| CBC | X | | | X | | | X | | | X | | | X | | | X | | | X | |
| LFTs | X | | | X | | | X | | | X | | | X | | | X | | | X | |
| cPRA | X | | | | | | | | | X | | | | | | | | | X | |
| BAFF/APRIL | X | | | | | | | | | X | | | | | | | | | X | |
| DSA Antibodies | X | | | | | | | | | X | | | | | | | | | X | |
| Bone Marrow Aspiration | | | | | | | | | | | | | | | | | | X ¹ | X ¹ | |

TABLE OF CONTENTS

| | |
|---|----|
| PROTOCOL SUMMARY..... | 3 |
| STUDY OVERVIEW DIAGRAM (optional)..... | 6 |
| SCHEDULE OF EVENTS..... | 7 |
| LIST OF TABLES AND FIGURES (OPTIONAL)..... | 11 |
| LIST OF ABBREVIATIONS AND GLOSSARY OF TERMS..... | 12 |
| 1. BACKGROUND AND STUDY RATIONALE | 13 |
| 1.1 Scientific Background | 13 |
| 1.1.1 Disease Under Treatment..... | 13 |
| 1.1.2 Ixazomib (MLN9708) | 14 |
| 1.2 Preclinical Experience | 14 |

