2. E-mail may be used throughout the course of the study for the purpose of scheduling study visits and notifying subjects of other study-related information.

Study Procedures

Screening Visit

The screening visit procedures will occur within a 30-day window prior to the Visit 1, Cycle 1 window (3-month window after screening). The following procedures will occur at the screening visit:

- Physical exam
- Medical history (including most recent cPRA results prior to enrollment)
- Vital Signs (Temperature, pulse, respirations, and blood pressure)
- Medication History
- Pregnancy Test (Serum HCG) for females of child-bearing potential
- CBC
- LFTs

Re-screening

Subjects who fail screening may be considered for re-screening if, in the opinion of the principal investigator, their clinical status has changed such that they may now be eligible for study participation per all eligibility criteria. At the discretion of the principal investigator, selected tests, such as lab tests, will not be repeated if previous screening results remain valid per the protocol-defined window for that test.

Visits: Patients will only receive one month's supply of ixazomib and dexamethasone and will return monthly for resupply. At each visit, they will be assessed for AEs by the study team. They will be examined by the principal investigator 5 times (please see tables 2-1 a-b and Figure 1, below): Days 1, 85, 169, 253, and 373 +6, - 3).

- Day 1: Prior to treatment initiation. H&P, Labs, Bone Marrow Aspirate
- Day 85 + 6, - 3: Prior to treatment dose. H&P, Labs
- Day 169 + 6, - 3 Prior to treatment dose. H&P, Labs
- Day 253 + 6, - 3 Prior to treatment dose. H&P, Labs
- Day 373 + 6, - 3 One month after treatment completion, H&P, Labs, Bone Marrow Aspirate
- Study drug will be dispensed at each month's in-person visit, prior the initiation of the next cycle, and after reviewing the AEs and monthly labs.

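### Serum hCG is tested only at screening, with no repeat at or near Day 1 and no single limit on the test's age; separately, Section 5.1 ends contraception at 30 days where other sections say 90

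*Combined protocol and SAP*

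**What the plan says.** **Testing.** In Table 2-1(a) the row reads "Pregnancy Test (where appropriate) | X", with its one mark in the Screening column. Table 2-1(b) carries the row "Pregnancy Test (where appropriate" again with no mark in it. The prose agrees with the tables. Section 4.1 lists "Pregnancy Test (Serum HCG) for females of child-bearing potential" under the screening visit and nowhere else. The test is absent from the Day 1 and monthly procedures and from the unscheduled and early-termination lists in Section 4.1. It is also absent from the final-visit procedures in Section 6.2 and the criteria for starting a new cycle in Section 6.3.1. Exclusion criterion 1 in Section 5.2 refers to a positive serum test in the screening period.

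**Timing.** Two neighbouring column headers in Table 2-1(a) give different limits: "Screening (<=/ 30 days" and "Cycle 1 (< /= 3 months after screening". Section 4.1 places screening "within a 30-day window prior to the Visit 1, Cycle 1 window (3-month window after screening".

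**Safeguards.**
- Contraception (two methods at once for women) or true abstinence: Protocol Summary, Sections 5.1 and 6.6.
- Investigator sign-off on eligibility before dispensing: Section 1.10.
- Documentation, before administration, that the dosing criteria are met: Section 6.2.
- Adverse-event questions before each cycle: Section 9.1.
- On examinations, Section 4.1 says "They will be examined by the principal investigator 5 times". Drug is released monthly, "after reviewing the AEs and monthly labs".
- A woman's duty to report even a suspected pregnancy and stop drug permanently: Section 8.3.

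**Contraception after the last dose.** Section 5.1 sets 30 days for women and for men. The Protocol Summary and Section 6.6 set 90 days for both. The reporting duty for women in Section 8.3 also runs 90 days.

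**The concern.** Section 6.6 states that the effect of ixazomib on human pregnancy is unknown, and Section 8.3 makes pregnancy a reason for permanent discontinuation. Women of childbearing potential are eligible from age 18. With the plan followed exactly, a woman who conceives between screening and Day 1 could take her first dose on the strength of an old negative result. CBC and LFTs are repeated on Day 1; hCG is not.

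The unclear age limit also matters for re-screening. Section 4.1 lets the investigator skip a repeat laboratory test if the earlier result is still within the protocol's window for that test. For hCG, that window cannot be read off the document.

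The contraception conflict is a separate matter of consistency. A participant who stops on day 31 after the last dose satisfies Section 5.1 and breaches Section 6.6.

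**Working it through.** The plan states no figure on this point to reproduce. The check is a reading of the schedule plus day counts.

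**1. Age of the only hCG result at first dose.** Taking a month as 30.4 days:

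| Reading | Source | Maximum age on Day 1 |
|---|---|---|
| 30-day limit governs | Screening header, Table 2-1(a) | 30 days |
| 3-month limit governs | Cycle 1 header, Table 2-1(a) | 3 × 30.4 = about 91 days |
| The two windows add | one reading of Section 4.1 | 30 + 91 = about 121 days |

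The documents do not say which reading applies.

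**2. Scheduled tests.** Screening 1; Day 1, 0; Cycles 2 to 12, 0; final visit, 0. The early-termination laboratory list in Section 4.1 does not include hCG.

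**3. What the safeguards cover after Day 1.** On-treatment examinations fall on Days 1, 85, 169 and 253. The gaps are 85 − 1 = 84, 169 − 85 = 84 and 253 − 169 = 84 days. Each gap spans 3 cycles × 3 doses = 9 ixazomib doses. Adverse-event questions come before every cycle, so contact is more frequent than examination. A footnote to Table 2-1(a) requires the Day 1 physical examination only if it was not done at screening, although Section 4.1 lists a history and physical on Day 1.

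**4. End of contraception, undelayed schedule.** The last scheduled dose in Table 2-1(b) is Day 323.
- Section 5.1: 323 + 30 = Day 353.
- Protocol Summary and Section 6.6: 323 + 90 = Day 413.
- Difference: 413 − 353 = 60 days.

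Day 353 is also 373 − 353 = 20 days before the Day 373 final visit.

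**5. Number affected.** The documents do not give the number of women of childbearing potential. With 10 participants, the assumed range is 0 to 10.

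**The case against.** A reader might infer that no woman is tested before her first dose. The documents do not support that: the screening test precedes dosing, and a positive result excludes. What is missing is a repeat at or near Day 1.

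A reader might also infer that the test will be three months old. That is one reading only. If the 30-day Screening header governs, the interval is an ordinary one and the Day 1 part of the point shrinks. What the documents establish is an ambiguous limit, and the ambiguity itself needs correcting.

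The strongest case for the plan is that it relies on prevention and reporting: contraception or abstinence from consent, sign-off before dispensing, documented dosing criteria, questions before each cycle, and a duty to report even suspicion of pregnancy. Table 2-1(a) as extracted also shows medical history on Days 113 and 141, and unscheduled visits are at the investigator's discretion. The eligibility checklist is not in the documents and the end of the screening period is not defined, so one cannot rule out that the sign-off prompts a fresh test in practice. This stands as a real reduction in risk. It does not replace a test, because no document requires one after screening.

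It is also tempting to say that the plan is deficient without monthly tests. No passage sets a frequency, so monthly testing is an option and its absence is not an error.

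On contraception, Section 5.1 is the outlier and 90 days is evidently intended. That supports the correction. It does not show that participants were told 30 days, since the consent form is not among the documents.

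**Conclusion.** Both parts hold, and both should be corrected.

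- **Testing:** one serum hCG at screening, no scheduled repeat at or near Day 1 or later, and an age limit at first dose that reads as 30, about 91 or about 121 days. The listed safeguards narrow the gap without closing it.
- **Contraception:** Section 5.1 conflicts with the Protocol Summary and Section 6.6 by 60 days for both sexes, and with the 90-day reporting duty for women in Section 8.3. Section 5.1 is the operative eligibility section, so its shorter period is the one a site would apply at enrolment.

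This rests on the current schedule tables and text, an undelayed schedule for the day counts, and an unknown number of women at risk between 0 and 10. No expected number of exposed pregnancies can be derived. The matter is one of participant safety and consistency; the primary efficacy analysis is not affected.

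**What to change.** **Core changes.**
1. For women of childbearing potential, add serum hCG to the Day 1 column of Table 2-1(a) and to the Day 1 procedures in Section 4.1. Require a negative result before first dispensing, and extend exclusion criterion 1 to cover that result.
2. State one maximum age for the screening hCG, and make the two headers in Table 2-1(a) and the screening text in Section 4.1 agree with it.
3. As a separate edit, change 30 to 90 days in inclusion criteria 3 and 4 of Section 5.1.

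**Cost.** The Day 1 test is one assay per woman of childbearing potential, 0 to 10 in total. It uses blood already drawn, with a possible short wait for the result and an occasional repeat of an unclear one. Section 4.2 counts a patient as enrolled only after the first treatment day, so a woman found pregnant before dosing would not use up one of the 10 places. The contraception edit asks nothing beyond what Section 6.6 already requires.

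**Optional.**
- hCG before each monthly dispensing, added to the Section 6.3.1 criteria. Including Day 1, that is 12 assays per woman completing 12 cycles, at most 12 × 10 = 120. Drug is already released one cycle (3 capsules) at a time, so each negative result would cover 3 doses.
- hCG at the final or early-termination visit, which cannot prevent dosing. One more test per woman makes 13, at most 130.
- Extension of the partner-pregnancy reporting clause in Section 8.3 to 90 days after the last dose.
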